## 8.2 Definition of Analysis Sets and Subgroups

The analysis sets of subjects whose data will be included in the analyses described in this IAP are defined in [Table 1](#).

**Table 1** Analysis Sets

Population	Description
Screening (SCR)	All subjects who sign informed consent.
DLT	All subjects who received at least one dose of study intervention and meet at least one of the following criteria: 

- Received at least 5 planned cumulative total daily doses of M4112 in the first cycle (first 28 days) or

- Experienced at least one DLT during the DLT period, regardless of the administered number of doses of study intervention/completion of the DLT period

Safety	The Safety Analysis Set will include all subjects who receive at least 1 dose of study treatment.
Concentration-QTc Analysis Set	The cQTc Analysis Set will include all subjects with at least baseline and one on treatment measurement of time-matched ECG and M4112 plasma concentration collected during the dose-escalation phase.
M4112 Pharmacokinetic	All subjects from the Safety Analysis Set without clinically important protocol deviations/violations or events that would affect PK (see Section 8.1 ). Subjects in the PK Analysis Set must have received at least 1 dose of M4112 and must have sufficient M4112 plasma concentration data to enable the calculation of at least 1 PK parameter. Sufficient concentration data is defined as at least 3 valid, postdose concentration points in the PK profile to obtain any PK parameter.
Pharmacodynamics	All subjects who received at least 1 dose of M4112 and provide the predose and at least 1 postdose sample for Pd assessment.

cQTc = concentration-QTc response; DLT = dose-limiting toxicities; ECG = electrocardiogram;

Pd = pharmacodynamics; PK = pharmacokinetic; QTc = corrected QT interval.

There are no subgroup analyses planned for this study.

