### DLT Definition

DLTs will be used to determine dose escalation, dose de-escalation, and the MTD (if reached), using the National Cancer Institute (NCI) Common Terminology Criteria for Adverse Events Version 4.03 (CTCAE 4.03). DLTs are defined in Section [6.2.4](#).

All subjects treated in dose escalation cohorts who miss > 5 planned total daily doses of M4112 **CCI** in the first cycle (first 28 days) of the dose escalation part for other than safety reasons are not eligible for DLT assessment, will not be considered in the Bayesian model and will not formally be replaced. If no evaluable subject from a cohort is left, the SMC will still convene to decide upon the continuation of the study and the number of subjects for the next cohort.

Subjects with nausea and vomiting will maintain normal schedule without re-dosing.

The MTD is defined by the SMC. An MTD is suggested from the Bayesian logistic regression model with DLT target rate of 30%.

Subjects who tolerate M4112 **CCI** without significant clinically relevant toxicities will continue to receive their assigned dose until discontinuation criteria are met, withdrawal of consent or the study ends, whatever occurs first (see Section [5.5.1](#) for exceptions).

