- Any Grade  $\geq 3$  clinical signs and symptoms related to increased QTc
- Evidence of hepatocellular toxicity attributable to study drug, such as increase in AST or ALT  $\geq 5$ -fold ULN for at least or  $\geq 3 \times$  ULN elevation of ALT or AST and elevation of serum total bilirubin to  $\geq 2 \times$  ULN, without initial findings of cholestasis (elevated serum ALP) or other apparent clinical causality (eg, viral hepatitis A, B, C, or co-medication).

If the above criteria are met, subjects should undergo close observation, including monitoring for symptoms (clinical signs of hepatitis, hypersensitivity, fatigue, decreased appetite, nausea, vomiting, abdominal pain, jaundice, fever, or rash) and hepatic function (AST, ALT, ALP and fractionated bilirubin) at least every 3 days, until symptoms and/or hepatic function abnormalities resolve, stabilize or return to baseline values. This event should be reported to the Sponsor within 24 h of learning of its occurrence.

Subjects experiencing DLTs during the DLT observation period (applicable for Part I only) as described in Section 6.2.4 will not receive further protocol therapy. Subjects with nausea and vomiting will maintain normal schedule without re-dosing.

In addition, any immune-related toxicity event observed in the next cycle will be reviewed and taken into account by the SMC for the overall evaluation of the safety and proposal of dose escalation of M4112 **CCI**.

All subjects treated in dose escalation cohorts who miss > 5 planned total daily doses of M4112 **CCI** in the first cycle (first 28 days) of the dose escalation part for other than safety reasons are not eligible for DLT assessment, will not be considered in the Bayesian model, and will not formally be replaced.

The MTD is defined by the SMC. An MTD is suggested from the Bayesian logistic regression model with target toxicity of 30%.

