- Immunotherapy including interferon, immunosuppressive drugs (eg, chemotherapy or systemic corticosteroids except for short term treatment of allergic reactions, endocrine replacement therapy at low dose prednisone [ $\leq 10$  mg daily] or equivalent, or for the treatment of irAEs or other appropriate short term steroid use), or other experimental pharmaceutical products. Short term administration of systemic steroid or other immunosuppressant such as infliximab or mycophenolate (ie, for allergic reactions or the management of irAEs) is allowed. Steroids with no or minimal systemic effect (topical, inhalation) are allowed.  
Note: for subjects with glioblastoma, steroid use is allowed

- Adefovir
- Prophylactic use of corticosteroids for infusion related reactions is prohibited
- Any live vaccine therapies for the prevention of infectious disease within 28 days prior to study entry and during study. Administration of inactivated vaccines is allowed (eg, inactivated influenza vaccines)
- Blood transfusions and erythroid growth factors are not allowed during the 28-day DLT window during the escalation phase. These subjects are considered to have had a DLT if the drop in hemoglobin is rated as drug related, or subjects are regarded as not evaluable, if the event is not related to study medication.

If the administration of a nonpermitted concomitant drug becomes necessary during the study, the subject will be withdrawn from study treatment (the Medical Monitor should be contacted to discuss whether the IMP must be discontinued).

[figure not shown]

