## 8.4 Analysis Sets

For purposes of analysis, the following populations are defined in Table 13. CCI

Table 13 Analysis Sets

Population	Description
Screening	All participants who sign informed consent.
Dose Escalation	All subjects treated in dose escalation cohorts who do not miss > 5 planned total daily doses of M4112 CCI in the first cycle (first 28 days) of the dose escalation part for other than DLT. The CCI
Safety	The Safety Analysis Set will include all subjects who receive at least 1 dose of study treatment. CCI
Concentration-QTc Analysis Set	The cQTc Analysis Set will include all subjects with at least baseline and one on treatment measurement of time-matched ECG and M4112 plasma concentration collected during the dose-escalation phase. The cQTc analysis set will be used for slope analysis of exposure response in QTc analysis.
M4112 Pharmacokinetic	All subjects from the Safety Analysis Set without major protocol deviations/violations or events that would affect PK. Subjects in the PK Analysis Set must have received at least 1 dose of M4112 and must have sufficient M4112 plasma concentration data to enable the calculation of at least 1 PK parameter. Sufficient concentration data is defined as at least 3 valid, postdose concentration points in the PK profile to obtain any PK parameter.
Pharmacodynamics	All subjects who received at least 1 dose of M4112 and provide the predose and at least 1 postdose sample for PD assessment.

ADA = anti-drug antibody; cQTc = concentration-corrected QT interval (QTc); DLT = dose-limiting toxicities; ECG = electrocardiogram; PD = pharmacodynamics; PK = pharmacokinetic.

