**CCI**

**CCI**

If the SMC decides to change the dosing regimen, a separate model will be set up or the model extended to a partial order Continual Reassessment Method.

All subjects treated in dose escalation cohorts who miss  $> 5$  planned total daily doses of M4112 **CCI** in the first cycle (first 28 days) of the dose escalation part for other than safety reasons are not eligible for DLT assessment, will not be considered in the Bayesian model and will not formally be replaced. The SMC can still be adjourned and the Bayesian model will be updated with the data from the evaluable subjects.

The target probability for the MTD suggested by the model will be 30%. If the DLT probability of a potential MTD reaches sufficient precision, the SMC will be informed.

The 2-parameter logistic regression model will be set up as follows:

The relationship between dose and toxicity rate is defined by:

$$P(DLT|d_j, \alpha, \beta) = \frac{\exp\left(\alpha + \exp(\beta) * \log\left(\frac{d_j}{d_{ref}}\right)\right)}{1 + \exp\left(\alpha + \exp(\beta) * \log\left(\frac{d_j}{d_{ref}}\right)\right)}$$

Where  $d_j \in \{100 \text{ mg}, 200 \text{ mg}, 400 \text{ mg}, 600 \text{ mg}, 800 \text{ mg}, 900 \text{ mg}\}$  (BID dosing) and  $(\alpha, \beta)$  are bivariate normally distributed and the reference dose ( $d_{ref}$ ) is 900 mg.

The following parametrization is chosen for the monotherapy prior:

$$E(\alpha) = -0.8001$$

$$E(\beta) = 0.4647$$

$$\text{Var}(\alpha) = 1.5^2, \text{Var}(\beta) = 1.5^2, \text{Cov}(\alpha, \beta) = 0$$

This would correspond to:

Dose	100 mg	200 mg	400 mg	600 mg	800 mg	900 mg
Prior mean DLT rate	9%	12%	17%	22%	29%	36%
Prior median DLT rate	1%	3%	7%	13%	22%	30%

DLT = Dose-limiting toxicity.

For more information on operating characteristics of the prior, see [Appendix V](#).

Posterior distribution and the recommended next dose level will be calculated using R version 3.1.2 or higher with library package bcrm [\(38\)](#) or package CRMPack or EAST version 6.4 or higher.

At interim analysis, after end of dose escalation, and main analysis, the number and proportion of subjects experiencing DLTs will be reported by dose level, based on observations during the first treatment cycle. Posterior probabilities (2.5%, 25%, 50%, 75%, and 97.5% quantiles) will be estimated.

The Dose Escalation Analysis Set will be used for this analysis.

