**10 Analysis Sets**

Analysis sets relevant to SMCs are defined in Table 1.

**Table 1** Analysis Sets

Population	Description
Screening	All participants who sign informed consent.
Dose Escalation	All subjects treated in dose escalation cohorts who do not miss > 5 planned total daily doses of M4112 CCI in the first cycle (first 28 days) of the dose escalation part for other than DLT. The latter only applies to subjects in the combination dose escalation.
Safety	The Safety Analysis Set will include all subjects who receive at least 1 dose of study treatment. In case of combination treatment, study treatment includes also the combination agents.
M4112 Pharmacokinetic	All subjects from the Safety Analysis Set without major protocol deviations/violations or events that would affect PK. Subjects in the PK Analysis Set must have received at least 1 dose of M4112 and must have sufficient M4112 plasma concentration data to enable the calculation of at least 1 PK parameter. Sufficient concentration data is defined as at least 3 valid, postdose concentration points in the PK profile to obtain any PK parameter.
Pharmacodynamics	All subjects who received at least 1 dose of M4112 and provide the predose and at least 1 postdose sample for PD assessment.

ADA = anti-drug antibody; cQTc = concentration-corrected QT interval (QTc); DLT = dose-limiting toxicities; ECG = electrocardiogram; PD = pharmacodynamics; PK = pharmacokinetic.

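### The final analysis plan counts a subject without a DLT as evaluable after 5 daily doses received, where the protocol excludes anyone who missed more than 5, and its list of changes does not say so

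*SAP*

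**What the plan says.** **Protocol.** Section 6.2.4 addresses "All subjects treated in dose escalation cohorts who miss > 5 planned total daily doses of M4112" in the first 28 days. Section 5.1 (DLT Definition) says that subjects who do so "for other than safety reasons are not eligible for DLT assessment", and Section 8.5.2 adds that they "will not be considered in the Bayesian model and will not formally be replaced". Table 13 in Section 8.4 builds the Dose Escalation set on the same count of missed doses, but words the exemption differently: "of the dose escalation part for other than DLT".

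**SMC analysis plan (appended to the SAP).** Table 1 in its Section 10 keeps the protocol rule: "All subjects treated in dose escalation cohorts who do not miss > 5 planned total daily doses of M4112". Its Section 9 declares no changes.

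**Final SAP (the integrated analysis plan).** Table 1 in Section 8.2 renames the set the DLT set. A treated subject enters by either of two routes. The first is to have "Received at least 5 planned cumulative total daily doses of M4112 in the first cycle". The second is to have "Experienced at least one DLT during the DLT period, regardless of the administered number of doses". Section 15.1 uses this set for the number and proportion of subjects with a DLT by dose level, and for posterior quantiles from the protocol's Bayesian logistic model. Section 7, which lists departures from the protocol, says that the set was renamed and its definition updated by way of clarification. It gives no threshold, old or new.

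**The concern.** The protocol counts doses missed and the final SAP counts doses received, yet both use the number 5. The two rules are far apart. A subject who took drug for 5 days, stopped for a non-safety reason and had no DLT is excluded under the protocol. Under the SAP the same subject is an evaluable subject without a DLT.

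The set feeds the primary endpoint. The SAP names the protocol's model but, read literally, gives it subjects whom Protocol 8.5.2 keeps out of that model. Someone with little exposure has had little chance to show a toxicity, so counting that person as DLT-free pulls the estimated rate down. With cohorts of about 3, one subject matters. A reader of Section 7 would not learn that the evaluability rule had moved.

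**Working it through.** **Step 1: the threshold.** Inputs: a 28-day first cycle and the number 5 in each rule. Assumption: one total daily dose per calendar day.

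- Protocol: at most 5 missed, so at least 28 − 5 = 23 received; 23/28 = 82.1%.
- Final SAP: at least 5 received; 5/28 = 17.9%.
- Newly admitted: non-exempt subjects without a DLT who received 5 to 22 daily doses, which is 22 − 5 + 1 = 18 possible counts.

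**Step 2: the model.** From Protocol 8.5.2 and Section 16.1 of the SMC plan:

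- logit P(DLT at dose d) = α + exp(β) × log(d/900)
- E(α) = log(0.31/0.69) = −0.8001
- E(β) = log[(log(0.11/0.89) − log(0.31/0.69)) / log(400/900)] = 0.4647
- both variances 1.5², covariance 0; binomial likelihood

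The posterior was obtained by numerical integration over a fine (α, β) grid reaching six prior standard deviations either side of the means.

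**Step 3: reproduce a printed result.** Protocol Appendix V, scenario 3a (0/3 at 100 mg, 0/3 at 200 mg, 1/3 at 400 mg) prints 0.60 / 0.31 / 0.09 / <0.01 for under-, target, over- and excessive dosing at 400 mg. The calculation gives 0.598 / 0.314 / 0.087 / 0.001, so the model is set up as the protocol intends.

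**Step 4: add one under-exposed subject without a DLT.** The documents give no subject counts, so these are illustrations. Dose 400 mg, with 0/3 at both 100 mg and 200 mg.

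| Protocol set → SAP set | Observed rate | Posterior median | 97.5% quantile |
|---|---|---|---|
| 1/5 → 1/6 | 20.0% → 16.7% | 0.111 → 0.101 | 0.385 → 0.355 |
| 1/2 → 1/3 (small-cohort extreme) | 50.0% → 33.3% | 0.159 → 0.139 | 0.520 → 0.466 |
| 0/2 → 0/3 | 0% → 0% | 0.017 → 0.014 | 0.273 → 0.242 |

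With no DLT at the level, the observed proportion stays at 0% but the posterior still falls.

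**Step 5: other dose levels.** Keeping 0/3 at every lower dose and moving the tested level across 100 to 900 mg, the median falls by 0.010 to 0.018 for 1/5 → 1/6 and by 0.020 to 0.063 for 1/2 → 1/3. The 0.063 arises only at 100 mg, where no lower dose has been tested.

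**The case against.** The strongest reply is that little may follow. The final analysis is abbreviated and descriptive (SAP Sections 6 and 9), no document shows a subject with 5 to 22 daily doses, and in the six-subject illustration the median moves by about 0.01 inside a 95% interval of roughly 0.01 to 0.39. All of this stands. It limits the weight of the point but does not make the two rules agree.

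Four stronger readings are tempting, and the documents do not support them.

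- *The change was deliberate.* The wording may be a drafting slip for missing no more than 5. Nothing shows intent. A programmer would still implement the text as printed.
- *Escalation advice was affected.* The SMC plan keeps the missed-dose rule, so the planned dose recommendations do not use the new threshold.
- *The second route into the set is another break with the protocol.* It largely restates the DLT exemption in Protocol Table 13 and agrees with Section 16.1 of the SMC plan, which uses subjects who complete the DLT period or have a DLT. It goes beyond the protocol's literal text only for a subject with a DLT who missed more than 5 daily doses for another reason, which is a remote case.
- *The protocol-defined results would be lost.* The dosing listing in SAP Section 13 would let a reader largely rebuild the counts, and the model, prior and example code are printed, so the quantiles could be recomputed.

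The two exemption wordings, and the transfusion rule in Protocol 6.5.2 under which "subjects are regarded as not evaluable, if the event is not related to study medication", are gaps within the protocol itself. They are not evidence about the changed threshold. The exemption wording matters here only because the corrected criterion cannot be programmed until one is chosen.

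**Conclusion.** The point holds for the first route into the DLT set and for its description in Section 7. As written, the final SAP lowers the minimum exposure for a non-exempt subject without a DLT from 23 to 5 of 28 daily doses, in the set used for the primary DLT analysis, and presents this as a clarification.

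Each such subject lowers the estimate: by about 0.01 in the posterior median in the six-subject illustration at 400 mg, and by 0.020 in the small-cohort extreme at the same dose. A reader might infer that the reported DLT rate will be understated. The documents do not support that, because the number of affected subjects is not given and may be zero, in which case nothing changes. The calculation assumes one total daily dose per day, one added subject and no DLT at lower doses. If doses missed for any safety reason are exempt, fewer subjects are newly admitted than if only a DLT exempts. This should be fixed, but it does not call the escalation into question.

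**What to change.** 1. In SAP Section 8.2, rewrite the first criterion so that a subject without a DLT is counted only if no more than 5 planned total daily doses of M4112 were missed in the first 28 days, apart from doses missed for the exempted reason. State that reason in the SAP. The protocol uses safety reasons in Sections 5.1, 6.2.4 and 8.5.2 but DLT in Table 13; the sponsor must reconcile them.
2. Keep the second criterion. Note in Section 7 that it also covers a subject with a DLT who missed doses for another reason.
3. Replace the clarification sentence in Section 7 with a statement of the actual change.
4. If the 5-dose threshold is intended, justify it in Section 7 and also report DLT proportions and posterior quantiles on the protocol-defined set.

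The cost is one criterion, a short passage in Section 7, one programming condition and agreement on the exemption; keeping the new threshold adds a second run of the DLT tables. A few subjects may leave the denominator, so the quantiles would widen and the reported DLT rate might look slightly less favourable.

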### Pharmacokinetics:

- Pharmacokinetic parameters for M4112 will be based on plasma concentrations collected predose and at 0.5, 1, 2, 3, 4, 6 and 8 h postdosing on Days 1 and 15 of Cycle 1. Predose concentrations on Day 8, Cycle 1 and predose and 2 h postdose on Day 1, Cycle 2 will be assessed.
- CCI [REDACTED]

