#### 7.5 Pharmacokinetics

Venous blood samples (4mL each) will be collected for analysis of M4112 in plasma by a validated LC-MS/MS assay. Full details of the bioanalytical method used will be described in a separate bioanalytical report.

The schedules for PK blood sampling are shown for M4112 administered as single agent (Table 4), CCI

PK parameters for M4112 will be calculated predose and over 8 h postdosing on Day 1 and Day 15, with a predose sample collected on Day 8 and predose and 2 h postdosing samples collected on Day 1 of Cycle 2.

Following analysis of M4112 concentrations, remaining plasma may be used for evaluation of potential metabolites.

CCI

The exact date/time of sample collection will be recorded in the eCRF. Although every effort should be made to collect PK blood samples according to the schedule, blood samples collected outside of the planned window are not to be considered protocol deviations as long as the actual collection time is recorded, with the exception of the predose samples, which will be considered a deviation if not collected predose.

The PK sample should be collected after ECG and vital signs are collected when scheduled at the same time.

Details of blood sample labeling, processing, storage, and shipment requirements will be described in a separate laboratory manual.

For each subject participating in the M4112 single agent dose escalation phase, a total of approximately 76 mL of blood (4 mL/sample; 19 samples over Cycle 1 and Cycle 2, Day 1) will be collected for determination of the M4112 plasma concentration.

CCI

CCI

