**Significance level:**

There is no formal significance level for this study and all analyses are considered descriptive.

**Presentation of continuous and qualitative variables for Demographics and Other Baseline Characteristics, Efficacy, and Safety:**

Continuous variables will be summarized using descriptive statistics, i.e.

- number of subjects (N), number of nonmissing values (n)
- mean, standard deviation
- median, 25th Percentile - 75th Percentile (Q1-Q3), minimum, and maximum

If there are no missing values this should be indicated by a 0.

Qualitative variables will be summarized by counts and percentages.

Unless otherwise stated, the calculation of proportions will be based on the number of subjects of the analysis set of interest. Therefore, counts of missing observations will be included in the denominator and presented as a separate category.

In case the analysis refers only to certain visits, percentages will be based on the number of subjects still present in the study at that visit, unless otherwise specified.

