### 16.1.2 Plasma Pharmacokinetic Parameters

Pharmacokinetic parameters will be calculated using standard noncompartmental methods and the actual administered dose. Pharmacokinetic parameters will be calculated using the actual elapsed time since dosing, given with a precision of 14 significant digits. In cases where the actual sampling time is missing, calculations will be performed using the nominal time. Otherwise, there will be no further imputation of missing data.

The following parameters will be calculated from M4112 plasma concentrations on the study days specified.

Symbol	Definition
AUC 0-8	The area under the concentration-time curve (AUC) from time zero (= dosing time) to 8 hours postdose, calculated on C1D1 and C1D15. Calculated using the mixed log linear trapezoidal rule (linear up, log down).
AUC 0-8 /Dose	The dose-normalized AUC 0-8 , calculated on C1D1 and C1D15. Normalized using the actual dose, using the formula AUC 0-8 /Dose.
C max	Maximum observed concentration, calculated on C1D1 and C1D15.
C max /Dose	The dose-normalized C max , calculated on C1D1 and C1D15. Normalized using the actual dose, and the formula C max /Dose.
t max	The time to reach the maximum observed concentration (in case of multiple/identical C max values, the first occurrence will be used), calculated on C1D1 and C1D15.
C pre	Predose (trough) observed concentration, calculated on C1D8, C1D15, and C2D1.
C pre /Dose	The dose-normalized C pre , calculated on C1D8, C1D15, and C2D1. Normalized using the actual dose, and the formula C pre /Dose.
R acc (AUC 0-8 )	The accumulation factor to assess the increase in exposure via AUC 0-8 following multiple dosing. R acc (AUC 0-8 ) = (AUC 0-8 after multiple dose [C1D15]) / (AUC 0-8 after single dose [C1D1]).
R acc (C max )	The accumulation factor to assess the increase in maximum concentration following multiple dosing. R acc (C max ) = (C max after multiple dose [C1D15]) / (C max after single dose [C1D1]).

For all dose-normalized parameters, no adjustment of dose (e.g., for molecular weight differences between salt and free form) is required as M4112 is not a salt.

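### The PK Analysis Set's minimum of three postdose concentrations does not fit the trough parameter Cpre and can exclude a subject whose troughs are valid (minor)

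*SAP*

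**What the plan says.** The PK Analysis Set in SAP Section 8.2, Table 1, has two adjoining data conditions. A subject "must have sufficient M4112 plasma concentration data to enable the calculation of at least 1 PK parameter". The next sentence defines what is sufficient: "Sufficient concentration data is defined as at least 3 valid, postdose concentration points in the PK profile to obtain any PK parameter". Protocol Section 8.4, Table 13, has the same sentence, and so does Table 1 of the Safety Monitoring Committee analysis plan appended to the SAP.

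SAP Section 16.1.2 lists Cpre among the parameters to be calculated: "Predose (trough) observed concentration, calculated on C1D8, C1D15, and C2D1". SAP Section 5.1 names Cpre and Cpre/Dose as secondary endpoints. SAP Section 7 explains that they replace the protocol's Cmin and Cmin/Dose, where Cmin was defined as a postdose minimum.

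The samples come from the Protocol synopsis and Section 7.5. Full profiles are "collected predose and at 0.5, 1, 2, 3, 4, 6 and 8 h postdosing on Days 1 and 15 of Cycle 1". The other two days are sparse: "Predose concentrations on Day 8, Cycle 1 and predose and 2 h postdose on Day 1, Cycle 2 will be assessed".

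SAP Sections 16.1.1 and 16.1.2 base all concentration and parameter summaries on the PK Analysis Set. Section 16.1.2 also fits a dose-proportionality power model to Cpre on each of its three days and includes a dose level only if it has at least 3 values of the parameter.

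**The concern.** The two conditions in Table 1 disagree. Cpre is a listed PK parameter and a single valid predose concentration yields it, so a subject with one valid trough passes the test of having at least one calculable parameter. The next sentence then refuses that subject, because it asks for three postdose values before any parameter counts as obtainable. The requirement suits parameters read from a profile but has no bearing on a trough.

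Trough concentration matters in this study: Protocol Section 5.1 gives a target Cmin over the dosing interval as the reason for twice-daily dosing. Cohorts are normally 3 subjects, so one subject left out through an unadapted rule can change what is reported for a dose level.

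**Working it through.** **1. Reproduce the schedule.** Inputs are Protocol Table 4, Section 7.5 and the synopsis.

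| Day | Predose | Postdose | Total | Cpre planned |
|---|---|---|---|---|
| C1D1 | 1 | 7 | 8 | no |
| C1D8 | 1 | 0 | 1 | yes |
| C1D15 | 1 | 7 | 8 | yes |
| C2D1 | 1 | 1 | 2 | yes |

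Sum: 8 + 1 + 8 + 2 = 19 samples; 19 × 4 mL = 76 mL. This matches Protocol Section 7.5 ("4 mL/sample; 19 samples over Cycle 1 and Cycle 2, Day 1", about 76 mL).

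**2. Compare what the rule asks with what Cpre needs.** The rule asks for 3 postdose values. Cpre needs 1 predose value and 0 postdose values. C1D8 and C2D1 have 0 and 1 postdose samples by design, so neither day can itself supply a three-point profile.

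**3. Apply the rule by subject.** Table 1 defines sets of subjects, so one qualifying profile is enough. I take the profile to be one day's curve, as in SAP Section 16.1.1, which plots concentration-time profiles for C1D1 and C1D15 only. A subject enters with at least 3 of 7 valid postdose values on C1D1 or on C1D15. Section 16.1.2 then calculates Cpre on all 3 planned days.

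**4. Who is excluded despite a valid trough?** A subject with at most 2 valid postdose values in every profile collected:
- sampled on both profile days: at least 7 − 2 = 5 of 7 values not valid on C1D1, and again on C1D15;
- stopped before C1D15: at least 5 of 7 not valid on C1D1.

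The remaining days cannot make this up: 0 + 1 = 1 postdose sample.

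**5. Effect on a dose level.** In a cohort of 3 with three valid troughs on a given day, excluding one subject leaves 3 − 1 = 2, below the 3 values required. The dose level then leaves the Cpre power model for that day. With 2 subjects in the set at that level, Section 16.1.2 also reduces the descriptive summary to n, minimum and maximum. At a dose level of 6, 6 − 1 = 5 remain and the level stays in the model. Protocol Section 8.1 anticipates 4 dose levels of 3 subjects and 2 of 6.

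**The case against.** The strongest defence is that the rule decides only who enters the set, and that the rest of the SAP makes the intention clear. Section 16.1.2 sets no three-point condition for Cpre, calculates it on all three days, and plans plots and power models for each. Where the SAP wants a condition on one parameter it says so there, as with the 8-hour sample for AUC0-8. This stands. It defeats the stronger reading that a reader might take from the word any, namely that Cpre cannot be derived on C1D8 and C2D1. That follows only if the test is repeated for each day or parameter. Table 1 does not say so, and Section 16.1.2 plans the opposite. The mention in Section 16.1.2 of excluded parameters does not establish that reading either, because Section 8.1 already allows affected PK data to be excluded.

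The defence also says that the remaining case is rare and of little consequence. Both profiles must largely fail while a trough survives. Section 8.1 generally keeps data despite sampling-time deviations, inadequate fasting, inaccurate dosing intervals and concomitant medication violations, and has other PK events judged case by case. Excluded values are still listed and flagged. The dose-proportionality analysis is exploratory, and "There is no formal significance level for this study and all analyses are considered descriptive". All of this stands and keeps the point minor. It does not remove the contradiction between the two sentences of Table 1, and being listed is not the same as being summarised or modelled.

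**Conclusion.** The rule is worded for profile-based parameters and does not fit Cpre or Cpre/Dose. Read by subject, it leaves Cpre available on C1D8, C1D15 and C2D1 for anyone with one usable C1D1 or C1D15 profile, so the documents do not support a claim that the trough endpoint is lost on any day. What remains is that a subject with valid troughs and no three-point profile is excluded from all PK summaries. In a cohort of 3, that takes the dose level from 3 values to 2 and out of each Cpre power model that the subject's trough would have completed.

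This rests on three assumptions: the test is applied by subject, a profile means one day's curve, and the other two subjects have valid troughs that day. The frequency is not stated in the documents and is probably low. Minor.

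**What to change.** In SAP Table 1, replace the single minimum with minimums by parameter:

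- **AUC0-8, Cmax, tmax, AUC0-8/Dose, Cmax/Dose and both Racc ratios:** at least 3 valid postdose concentrations in the profile concerned (for Racc, in both profiles). The 8-hour condition for AUC0-8 in Section 16.1.2 is unchanged.
- **Cpre and Cpre/Dose:** one valid predose concentration on the day concerned.
- **Set membership:** a subject enters if at least one parameter is obtainable under its own minimum. The dosing requirement and the exclusions for deviations or events affecting PK stay as they are.

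List the change in SAP Section 7 beside the replacement of Cmin by Cpre. Section 6 requires the plan to be approved before database lock. Settling the wording by then avoids deciding whose troughs count after the data are known. The cost is a few lines of text, with no new samples or data.
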